### 5.3 Considerations for study visits

Procedures visits should be scheduled as close to the indicated study days and study weeks as possible. See the Study Flow Chart in Section 7 for a complete listing of study procedures required at each visit.

### 5.4 Subject Withdrawal/Discontinuation Criteria

Subjects may withdraw consent at any time for any reason or be dropped from the trial at the discretion of the investigator should any untoward effect occur. In addition, a subject may be withdrawn by the investigator or the Sponsor if enrollment into the trial is inappropriate, the trial plan is violated, or for administrative and/or other safety reasons.

In this trial, a subject may discontinue from treatment but continue to participate in the regularly scheduled activities, as long as the subject does not withdraw consent. Discontinuation from treatment is permanent. Once a subject has discontinued treatment, even though he/she continues to be monitored in the trial, he/she shall not be allowed to begin treatment again.

A subject must be discontinued from the trial for any of the following reasons:

- The subject or legal representative (such as a parent or legal guardian) withdraws consent.
- Request of the subject (subjects have the right to discontinue treatment at any time for any reason).

A subject must be discontinued from treatment (but may continue to be monitored in the trial) for any of the following reasons:

- Subject meets any virologic failure criteria (see section 2.8.4 for definitions of virologic failure)
- Suicidal or homicidal ideation or attempt.
- Severe depression.

- Subject has a positive test for nonprescription opiates, methamphetamines, or cocaine.
- Subject becomes pregnant during the trial.
- A physician investigator feels it is in best interest of the subject to discontinue.
- The subject's ALT or AST increases to >500 IU/L.
- The subject's ALT or AST increases to >3x baseline, is >100 IU/L, and there is a simultaneous increase in total bilirubin >2x ULN and/or INR >1.5.
- The subject's ALT or AST increases to >3x the nadir value, is >100 IU/L, and there is a simultaneous increase in total bilirubin > 2x ULN and/or INR >1.5.
- The subject's ALT or AST increases to >3x baseline, is >100 IU/L, and is temporally associated with the new onset or worsening of any of the following adverse experiences that are of moderate or severe intensity and deemed by the investigator to be at least possibly related to EBV/GZR (50/100 mg): nausea, vomiting, right upper quadrant pain or tenderness, and/or eosinophilia (>5%).
- The subject's ALT or AST increases to >3x the nadir value, is >100 IU/L, and is temporally associated with the new onset or worsening of any of the following adverse experiences that are of moderate or severe intensity and deemed by the investigator to be at least possibly related to EBV/GZR (50/100 mg): nausea, vomiting, right upper quadrant pain or tenderness, and/or eosinophilia (>5%).
- The subject's alkaline phosphatase increases to >3x ULN, there is a simultaneous increase in total bilirubin > 2x ULN and other causes of elevated alkaline phosphatase are excluded.
- The subject's alkaline phosphatase increases to >5x ULN and other causes of elevated alkaline phosphatase are excluded.
- A subject **may** be discontinued from treatment for any of the following reasons:

SAE assessed by the physician investigator as possibly or probably related to study medication. Investigator may continue the subject in the trial, if it is deemed to be in the best interest of the subject to stay on the study treatment.

Failure to comply with the dosing, evaluations, or other requirements of the trial.

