#### 5.4.1 Subject Replacement Strategy

A subject that discontinues from the trial will not be replaced except if the subject is a screen fail or wrongly included. The screen fail rate is estimated at around 20%, so we plan to include about

145 patients in the study (patient who signed the informed consent form).

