### **8.1.5.3 Post Treatment Assessments**

The post treatment Week 4, 12 and 24 visits should be timed from the date of last administration of study drugs. All subjects must be complete the post treatment Week 4 and 12 visits. Subject with HCV RNA < LLOQ at the post treatment week 12 will complete the post treatment Week 24 visit, unless viral relapse is determined.

Female subjects of childbearing potential should be provided with Urine Pregnancy Test Kits, instructed on their use and requested to continue to self-monitor for pregnancy between scheduled study visits, every 4 weeks, for 6 months after their last dose of study drugs. If required by regulations, additional pregnancy test beyond 6 months may be added. The subject will be contracted every 4 weeks and asked to report results of the urine pregnancy tests.

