#### **8.1.5.4 Drug Administration**

Following completion of the Day 1 procedures and confirmation of eligibility, the site pharmacist or study coordinator will contact the Promotor for assignment of the drug to be administered.

Sites should not call the Promotor for drug administration until the subject has met all criteria for the study and is ready to receive the first dose of study medication on Day 1.

The first dose of prescribed study medications should be administered at the Day 1 visit. Subjects who discontinue therapy in the trial prior to the last scheduled treatment visit should have an Early Discontinuation visit and then continue with the follow-up visits.

At a minimum, collect the following information when a subject discontinues from the trial:

1. The reason the subject discontinued.
2. The date of the last dose of study medications from the trial.
3. The date of the last assessment and/or contact. A follow-up contact (telephone or visit) will be arranged as appropriate.

4. (Serious) Adverse events.
5. Final Assessments: Every effort should be made to ensure that all procedures and evaluations scheduled for the Early Discontinuation Visit are performed.
6. Retrieve all study medications from the subject.

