### **10.2 Statistical Analysis Plan Summary**

The analysis set for antiviral activity analyses will be the Full Analysis Set which includes subjects who were enrolled and received at least one dose of study drug and have naïve chronic genotype 1b HCV infection with non severe fibrosis.

Statistical analysis will be performed using Stata software (version 13; Stata-Corp, College Station, Tex., USA). All statistical tests will be two-sided and  $p < 0.05$  will be considered significant.

Qualitative variables will be described in terms of numbers and proportions.

Quantitative variables will be described in terms of numbers, mean  $\pm$  standard deviation or median [inter-quartile range] according to statistical distribution (normality studied using Shapiro-Wilk test).

Graphic representations will be complete presentations of results.

Sensitivity analyses will be considered to measure the possible impact of missing data on results and the more appropriate imputation method. For the analysis of post-baseline categorical efficacy endpoints, if a data point is missing and is immediately preceded and followed in time by values that are deemed successes, then the missing data point will be termed a success; otherwise the data point will be termed a failure. For example if a data point is missing and is preceded and followed in time by values that are <LLOQ target not detected (TND), then the missing data point will be set to < LLOQ TND.

Demographic and baseline measurements will be summarized using standard descriptive methods by treatment group and overall.

Exploratory analyses may be performed to assess the relationship between demographic, baseline characteristics, (including baseline viral load, age, sex, baseline ALT level, bodyweight, fibrosis score and additional endpoints as necessary) and antiviral activity (HCV RNA reduction, proportion of subjects with HCV RNA below the limit of quantification and target not detected at various time points during and following discontinuation of study drugs). Predictive factors of antiviral activities may be examined using regression type of analysis.

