### **10.4 Analyses for the secondary objectives**

Most of secondary analyses will be exploratory and will be performed as described previously (i) to evaluate the safety and tolerability of EBR/GZR treatment, (ii) to determine the proportion of subjects who attain SVR at 4 and 24 weeks after cessation of treatment (SVR4 and SVR24), (iii) to evaluate the proportion of subjects with virological failure and (iv) to evaluate the emergence of viral resistance to EBR/GZR during treatment and after cessation of treatment. Finally, to evaluate the kinetics of circulating HCV RNA during treatment and after cessation of treatment, a descriptive statistical analysis will be proposed. This analysis will be completed using random-effects models useful to evaluate kinetics taking into account between and within patient variability.

To better understand the potential for Resistance Associated Variants (RAVs) with EBR and/or GZR, samples will be retained from Day 1 and viral failure visits and RAVs will be assessed for any subject who has detectable virus above 1000 UI/mL and has met a virologic failure criteria. Subjects who discontinue the treatment will continue to participate in the scheduled follow-up activities including monitoring for resistance.

Exploratory IL28B genotyping may also be conducted to detect genetic variations associated with response to treatment of hepatitis C. A separate signature will be required to document a subject's agreement to provide additional samples for optional genetic research.

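### Section 5.4 makes a subject's own request to stop treatment a mandatory exit from the trial, against the rest of the protocol; followed literally, SVR12 is missing and scored a failure

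*Combined protocol and SAP*

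**What the plan says.** Section 5.4 has two mandatory lists. The first gives reasons for leaving the trial and has two bullets: withdrawal of consent (by the subject or a legal representative), and "Request of the subject (subjects have the right to discontinue treatment at any time for any reason"). The second gives reasons for stopping treatment, with continued monitoring allowed; it includes virologic failure, ALT/AST rises and pregnancy.

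Other text deals with people who stop treatment early:

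- Section 5.4, the paragraph before the lists: "a subject may discontinue from treatment but continue to participate in the regularly scheduled activities, as long as the subject does not withdraw consent".
- Section 8.1.5.3: "All subjects must be complete the post treatment Week 4 and 12 visits".
- Section 8.1.5.4, on subjects who stop therapy before the last scheduled treatment visit: they "should have an Early Discontinuation visit and then continue with the follow-up visits".
- Section 10.4: "Subjects who discontinue the treatment will continue to participate in the scheduled follow-up activities including monitoring for resistance".

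Three rules decide how such a subject is counted:

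- Section 10.2 defines the Full Analysis Set as "subjects who were enrolled and received at least one dose of study drug" and who have the target disease.
- Section 5.4.1: "A subject that discontinues from the trial will not be replaced except if the subject is a screen fail or wrongly included".
- Section 10.2 counts a missing categorical efficacy value as a success only when the values immediately before and after it are successes; "otherwise the data point will be termed a failure".

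**The concern.** The bullet's heading is about leaving the trial, but its explanation is about stopping treatment. Since withdrawal of consent is listed separately, the literal reading adds only one group: subjects who choose to stop tablets but still consent. The preceding paragraph keeps exactly that group in scheduled visits. Subjects stopped for the reasons in the second list are not affected.

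The primary endpoint of a subject removed this way is never observed. The early discontinuation visit gives HCV RNA only at the time of stopping, which says nothing about SVR12. Relapse timing and resistance data for that subject, both relevant to the secondary objectives, are lost as well. A site that follows 8.1.5.4 would instead record the observed result, so the same patient could be scored differently at two sites.

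**Working it through.** **Step 1. Trace one subject under each reading.** The subject has taken at least one dose, has the target disease, asks to stop tablets and does not withdraw consent.

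| Step | 5.4 bullet, read literally | 5.4 paragraph, 8.1.5.3, 8.1.5.4, 10.4 |
|---|---|---|
| Status | Must leave the trial | Off treatment, still in the trial |
| Early discontinuation visit | Yes | Yes |
| Post-treatment Weeks 4 and 12 | None | Both attended |
| Full Analysis Set (10.2) | Included | Included |
| Replaced (5.4.1) | No | No |
| SVR12 | Missing | Observed |
| Scoring | No later value exists, so the exception in 10.2 cannot apply: failure | As observed |

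**Step 2. Reproduce the plan's own figure.** Section 10.1 gives n = 120, assumed SVR12 of 96%, and an exact 95% lower bound above 91.5%. The exact (Clopper-Pearson) lower bound for x successes is the 0.025 quantile of Beta(x, n − x + 1). Now 0.96 × 120 = 115.2. Rounded up, 116/120 gives 91.69%, which reproduces the stated figure. Rounded down, 115/120 gives 90.54%, which does not. The bound therefore exceeds 91.5% only with at least 116 successes, that is, at most 4 failures of any kind.

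**Step 3. Effect of one cured subject scored a failure.** Lower bounds at n = 120:

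| Successes | Exact 95% lower bound | Loss from one fewer success |
|---|---|---|
| 117 | 92.87% | 1.18 points |
| 116 | 91.69% | 1.15 points |
| 115 | 90.54% | 1.11 points |
| 114 | 89.43% | not computed here |

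One such subject takes the bound across 91.5% only if exactly 116 would otherwise have succeeded. At a true SVR12 of 96%:

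P(X = 116) = C(120, 4) × 0.96^116 × 0.04^4 = 8,214,570 × 0.008779 × 0.00000256 = 0.185.

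This is conditional on the event having happened. It is not the probability of harm.

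**Step 4. Chance of a bound above 91.5%, for an assumed number of affected subjects.** With every subject at 96%, P(X ≥ 116 of 120) = 47.3%. If k subjects are scored failures for this reason and the other 120 − k are at 96%, it is 29.5% for k = 1, 14.5% for k = 2 and 5.0% for k = 3. The documents do not supply k.

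**Step 5. Can the documents supply a rate?** In the earlier ribavirin-free 8-week arm (section 2.7 and Annexe 1), 29 SVR + 2 relapses = 31, so 0 of 31 lacked an outcome. The exact two-sided 95% upper limit is 1 − 0.025^(1/31) = 11.2%. That is too wide to be useful. A footnote to the SVR12 figure in Annexe 1 mentions one patient who stopped early for a reason other than an adverse event or virologic failure, but does not say it was by own request.

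**The case against.** The best counter-argument is that, under a heading about leaving the trial, a subject's request most simply means a request to leave. The bullet would then nearly duplicate the consent bullet, and this protocol repeats itself elsewhere (several laboratory exclusions appear more than once). On that reading nothing conflicts. The right handling is also stated in four places, so harm needs a site to prefer one parenthesis to all of them and turn away a willing subject. Finally, someone who stops before the end of an already shortened course may truly fail, in which case scoring a failure is correct.

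Much of this stands as an argument about frequency. The number affected is probably very small, and Step 3 assumes a subject who would have been cured. It does not remove the defect. The parenthesis speaks of treatment, the list is mandatory, and 8.1.5.4 is worded only as a recommendation, so a careful site has grounds to end follow-up. If the subject would truly have failed, observing that failure with its timing and any resistance data is still better than imputing it.

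The missing-data rule sits in a paragraph of 10.2 that opens with sensitivity analyses, and 10.3 does not restate it. Its wording covers all post-baseline categorical efficacy endpoints, however, and no other rule is given for SVR12. The sensitivity analyses could show the effect of the imputation but cannot recover a sample that was not drawn.

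**Conclusion.** The concern holds. The bullet contradicts its own section and three others, and a subject handled by its literal wording loses the primary endpoint and is counted as a failure. This looks like a drafting slip rather than a decision to drop such subjects.

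The size is 1.1 to 1.2 percentage points on the exact lower bound for each cured subject affected, for totals between 114 and 117 of 120. This assumes that the site applies the bullet literally, that the subject would have reached SVR12, and that the 10.2 rule governs the primary analysis. The rate of own-request stopping is unknown and probably low. The 91.5% figure is planning precision and not a decision rule, so crossing it does not by itself change a formal conclusion. The change should be made because the lost data cannot be recovered and the correction costs very little.

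**What to change.** In section 5.4, move the bullet on the subject's request from the list of reasons to leave the trial to the list of reasons to stop treatment with monitoring allowed. Keep withdrawal of consent as the only subject-initiated reason to leave; the right to leave at any time is preserved.

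A subject who stops tablets by choice then has the early discontinuation visit and attends follow-up Weeks 4 and 12, timed from the last dose as 8.1.5.3 requires, and Week 24 if HCV RNA is below the LLOQ at Week 12. The observed HCV RNA is used for SVR4, SVR12 and SVR24.

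Replacing treatment with participation inside the parenthesis would also remove the contradiction, but it would leave two overlapping exit routes and would not list stopping by choice among the treatment-only reasons. Moving the bullet is clearer.

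The cost is one bullet in a protocol amendment. No visit or test is added, because 8.1.5.3 already requires the Week 4 and 12 visits of all subjects.

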**Table 6 : Trial Treatment**

Drug	Dose/Potency	Dose Frequency	Route of Administration	Regimen/ Treatment Period	Use
Grazoprevir(GZR) o	100 mg	QD	Oral	8 Weeks	Experimental
Elbasvir (EBV)	50 mg	QD	Oral	8 Weeks	Experimental

Elbasvir/Grazoprevir

Subjects will receive treatment with EBV/GZR (50/100 mg) fixed dose combination once-daily (QD) orally. Study therapy will be supplied once during the treatment period at Day 1. Subjects will be instructed to take their daily medications as instructed on the bottle labels.

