## 7 TRIAL FLOW CHART

Visit No.	1	2	3	4	5	6	7	8		
Study Period		Treatment Weeks				Follow-Up Wks			Unscheduled	
STUDY PROCEDURES	Scr	Day 1 	2	4	8	FU4	FU 12	FU 24	Unsched/ Viral Fail Conf Visit	Early Discon Visit
ADMINISTRATIVE PROCEDURES										
Informed Consent	x									
Inclusion/Exclusion Criteria	x									
Medical History	x									
Prior and Con-med Review	x	x	x	x	x	x	X	X	x	x
DRUG ADMINISTRATION										
EBV/GZR dispensation 		x								
EBV/GZR compliance 			x	x	x					
CLINICAL SAFETY EVALUATIONS										
Physical Examination 	x	x			x					x
Weight	x	x	x	x	x	x	x	x	x	x
Height	x									
Fibroscan®	x									
Vital Signs	x	x	x	x	x	x	x	x	x	x
Confirmation of Birth Control	x	x	x	x	x	x	x	x	x	x
Review (Serious) Adverse Events 	x	x	x	x	x	x	x	x	x	x
LABORATORY SAFETY EVALUATIONS										
Coagulation	x	x			x				x	x
Fibrotest®	x									
Chemistry & Hematology	x	x	x	x	x	x			x	x
HCV, HIV, HBV testing	x									
HCV Genotyping	x									
HCV RNA Level	x	x	x	x	x	x	x	x	x	X 
Urine Analysis	x									
Urine Pregnancy Test (females of child bearing potential only) 	x	x		x	x	x	x	x	x	x

-  A comprehensive PE will be done at screening and baseline (Day 1). For all other visits focused PE will be conducted if necessary
-  Review of Adverse Events should include collecting serious adverse events and Events of Clinical Interest throughout the study, and collecting all adverse events Day 1(post-dose) through 14 days following the last dose of study drug. Adverse events occurring prior to study drug administration or after study drug discontinuation, as a result of a protocol-specified procedure or intervention, should also be reported.
-  When study visits are spaced more than one month apart in the follow-up period, urine pregnancy test kits will be dispensed to female subjects of childbearing potential so that **monthly** pregnancy testing can continue for 6 months post dosing. The test results must be provided to the investigator and/or site personnel. Subjects should be instructed to contact the investigator and/or site personnel immediately if the result of the self-pregnancy test is positive.
-  Procedures on Day 1 should be performed prior to the first morning dose unless specified otherwise.
-  EBV/GZR will be provided at the baseline visit.

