### 8.1.3 Laboratory Safety Evaluations

Details regarding specific laboratory procedures/assessments to be performed in this trial are provided below. The total amount of blood to be collected by visits is between 45 to 75 mL over the course of the trial (from pre-trial to post-trial visits).

Coagulation: INR, Prothrombin time (PT) Activated partial thromboplastin time (APTT)

Hematology : Hematocrit, Hemoglobin (Hb), Platelet Count, Red blood celled count (RBC), White blood cell count (WBC) with differential (absolute and percentage) including Lymphocytes, Monocytes, Neutrophils, Eosinophils, Basophils, Reticulocytes count and MCV.

Chemistry : Alanine aminotransferase (ALT/SGPT), Aspartate aminotransferase (AST/SGOT), Albumin, Alkaline Phosphatase, Creatine Kinase, Creatinine, Total Bilirubin (reflex to Direct Bilirubin), Glucose, Lipase, Potassium, Sodium, Direct Bilirubin at screening only, Hemoglobin A1c (HbA1c), Fibrotest®, Urea, Hyaluronic Acid.

Virological Tests : Serologies for HCV, HBV and HIV. HCV RNA will be measured using the Cobas® Taqman® HCV Test, v2.0 for use with Ampliprep. HCV genotype and subtype will be determined using classic local process. Samples for HCV genotype evaluation must be obtained as part of the main consent for inclusion in the study in each local laboratory

Blood must be drawn from each subject as part of the main consent to assess HCV RNA plasma levels at various time points as shown in the flow chart. HCV-RNA in plasma will be measured using a COBAS™ Taqman™ HCV Test, v2.0 ® assay for use with the High Pure System with a lower limit of detection and quantification of 15 IU/mL or using ABBOTT Amplification Reagent Real Time HCV with limit of detection and quantification of 12 IU/mL.

Urinalysis : Appearance, Blood, Color, Glucose, Leukocyte esterase, pH, Protein, Urobilinogen, Reflex to microscopic urinalysis if dipstick result is abnormal.

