#### **8.1.5.2.2 Week 2 (visit 3 + 3 days)**

The following procedures must be completed at the end of Week 2

- Obtain vital signs
- Assessment of AEs and concomitant medications
- Obtain blood samples for :  
Hematology and chemistry  
HCV RNA
- Review study drug compliance and drug administration instruction with subject

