#### **8.1.5.2.4 Week 8 (visit 5 + 3 days)**

The following procedures must be completed at the end of Week 8:

- Perform complete physical examination
- Obtain body weight
- Obtain vital signs
- Assessment of AEs and concomitant medications
- Obtain blood for :  
Hematology and chemistry  
Coagulation  
HCV RNA
- Confirmation of birth control
- Obtain urine sample for :  
Beta-HCG pregnancy test for females of childbearing potential only
- Review study drug compliance and drug administration instruction with subject
- Complete medication pill count

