### 9.3 Packaging and Labeling Information

ZEPATIER® (elbasvir and grazoprevir) is a fixed-dose combination tablet for oral administration containing 50 mg of elbasvir and 100 mg of grazoprevir. The beige and oval shaped film-coated tablets bear the inscription "770" on one side and are smooth on the other. ZEPATIER® is available in two blister packs of 28 tablets.

Clinical supplies will be affixed with a clinical label in accordance with regulatory requirements.

Subjects will receive Open Label EBR(50mg)/GZR(100mg) at the baseline visit.

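### Two mandatory liver stopping rules can be met on INR alone, but no INR is required at Week 2 or Week 4

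*Combined protocol and SAP*

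**What the plan says.** Section 5.4 lists reasons for which a subject must come off treatment. Two of them combine an aminotransferase rise with a sign of impaired liver function: ALT or AST above three times baseline (first rule) or above three times nadir (second rule), and in each case the value "is >100 IU/L, and there is a simultaneous increase in total bilirubin >2x ULN and/or INR >1.5".

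Section 8.1.3 places INR in the coagulation panel, not in chemistry or hematology. Section 5.3 gives the flow chart the governing role: "See the Study Flow Chart in Section 7 for a complete listing of study procedures required at each visit". The flow chart marks coagulation at screening, Day 1, Week 8, the column headed "Unsched/ Viral Fail Conf Visit", and early discontinuation. The Week 2 and Week 4 cells are blank. The visit lists agree: at Week 2 (8.1.5.2.2) the blood draw is "Hematology and chemistry" plus HCV RNA, and Week 4 (8.1.5.2.3) is the same. Coagulation returns in the Week 8 list (8.1.5.2.4).

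Section 8.1.3 does provide one reflex blood test, "Total Bilirubin (reflex to Direct Bilirubin"), but none that leads to an INR. Section 2.5 advises stopping the drug when an ALT rise is accompanied by a rising INR.

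**The concern.** A mandatory stopping rule works only if each quantity that can trigger it is measured while stopping is still possible. Here the enzymes and bilirubin are measured at every on-treatment visit, but INR is not measured between the pre-dose Day 1 sample and the end of the course. A patient at Week 2 or Week 4 with enzymes above the threshold, bilirubin not above 2x ULN and an INR above 1.5 meets a mandatory stop. A site that follows the protocol to the letter would not know it. This is a matter of patient safety; the primary endpoint is not touched.

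**Working it through.** No sample-size or power figure bears on this point. The check sets the stopping rule against the schedule and then works out how wide the gap is.

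**1. When each component is scheduled** (Section 7, read with 8.1.3 and 8.1.5.2)

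| Visit | ALT/AST, total bilirubin (chemistry) | INR (coagulation) |
|---|---|---|
| Screening | yes | yes |
| Day 1, pre-dose | yes | yes |
| Week 2 | yes | **no** |
| Week 4 | yes | **no** |
| Week 8 | yes | yes |
| Unscheduled | yes | yes |
| Early discontinuation | yes | yes |

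After Day 1 and before the end of treatment, chemistry is scheduled at 2 of 2 visits and INR at 0 of 2. The flow chart and the visit lists agree, so this is not a table-reading artefact.

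**2. Whether the Week 8 INR helps.** "Study therapy will be supplied once during the treatment period at Day 1" (Table 6), and the product "is available in two blister packs of 28 tablets" (Section 9.3). Supply is 2 × 28 = 56 tablets = 8 × 7 days. The Week 8 list opens with "The following procedures must be completed at the end of Week 8", so that result arrives when there is little or no treatment left to stop.

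**3. Whether another rule forces an INR earlier**

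- *Unscheduled visits.* The flow chart marks coagulation there, while 8.1.5.2.5 leaves the assessments to the investigator. Whichever governs, no ALT/AST value obliges anyone to call the visit. Extra testing (8.1) and recall (2.8.5) are optional.
- *Section 8.1.6.* The weekly return visits apply to laboratory values of clinical interest at the last dosing visit. The rest of the section defers to the flow chart.
- *Section 8.2.3.2.* A first value above three times baseline and above 100 IU/L must be reported within 24 hours. That is a report, not a test, and there is no matching entry for nadir.
- *Early discontinuation visit.* Its coagulation sample follows the decision to stop.
- *Synopsis.* It mentions on-treatment safety laboratory tests without naming coagulation, although it names coagulation for screening.

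**4. Width of the exposed window.** Section 5.4 also stops treatment for ALT or AST above 500 IU/L alone. The INR limb therefore matters only when

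3 × baseline < ALT/AST ≤ 500, so baseline < 500/3 = 166.7 IU/L,

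and likewise for nadir. The 100 IU/L floor is the binding lower limit when baseline is below 100/3 = 33.3 IU/L. Table 5 excludes ALT or AST only above 350, so baselines below 167 are eligible. The nadir-only case arises essentially at Week 4, because at Week 2 only the screening and Day 1 values come before it.

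**5. Likely frequency.** In Annexe 1 (8 weeks, no ribavirin), ALT above 2.5x baseline was 0/31 and AST above 2.5x baseline was 0/31. Section 2.5 reports ALT rising from normal to above 5x ULN in under 1%, generally at or after Week 8. Neither threshold is the one in Section 5.4, and the Annexe figures carry no 100 IU/L floor. They suggest that few patients would be affected but do not bound the number.

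**The case against.** The strongest reply is that a practical route to an INR exists. The enzyme limb of the baseline rule is itself a 24-hour reportable event. The sponsor or investigator can then call an unscheduled visit, where the flow chart marks coagulation, and same-day eCRF entry supports central safety monitoring (14.1). An investigator applying a mandatory rule cannot properly conclude that its INR limb is unmet without an INR, so what is missing may be only explicit wording. The gap is also narrow: bilirubin and the 500 IU/L stop work fully at both visits, screening excludes raised INR and severe fibrosis, and the documents place notable ALT rises mostly at or after Week 8. Finally, the rule requires a simultaneous increase, and a later recall INR may not obviously qualify.

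Much of this stands. The gap is small, the safeguards reduce the risk, and the simultaneity point bears on how the fix is worded. But each step towards an INR is discretionary, the reporting rule does not cover the nadir case, and the Week 8 INR comes too late to stop treatment. A mandatory criterion should not depend on someone choosing to order the test.

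**Conclusion.** The concern holds. INR is scheduled at 0 of the 2 visits at which stopping would still be useful, and both INR-containing rules are affected. The exposure needs all of the following together: enzymes above three times baseline or nadir and above 100 but not above 500 IU/L; bilirubin not above 2x ULN; INR above 1.5; no qualifying symptoms or eosinophilia; no other stopping rule met; and no INR ordered on the investigator's or sponsor's initiative. That is likely to be rare, and the documents do not allow a count. The conclusion assumes that sites perform the scheduled and required tests and nothing more. It is worth correcting because the remedy is cheap and the rule protects patients; it has no bearing on SVR12.

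**What to change.** Preferred: add a sentence to Section 5.4, repeated as a footnote to the flow chart, along these lines:

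> *If ALT or AST is >3x baseline or >3x nadir and >100 IU/L at any on-treatment visit, INR must be measured promptly and the stopping criterion assessed on the result.*

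The sponsor should also set a time limit for that INR and state that a result within it counts as simultaneous. The cost is one sentence and one footnote. Few tests are expected, but some patients may need a recall visit because no coagulation sample is drawn at Weeks 2 and 4.

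Alternative: mark coagulation at Weeks 2 and 4 in the flow chart and in 8.1.5.2.2 and 8.1.5.2.3. This gives a truly simultaneous INR without recall, at a cost of one extra tube per patient per visit, at most 2 × 120 = 240 tests, at visits where blood is already taken.
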